9.1 Data confidentiality

Information about study subjects will be kept confidential and managed under the applicable laws and regulations. Those regulations require a signed subject authorization informing the subject of the following:

- What protected health information (PHI) will be collected from subjects in this study
- Who will have access to that information and why
- Who will use or disclose that information
- The rights of a research subject to revoke their authorization for use of their PHI.

In the event that a subject revokes authorization to collect or use PHI, the investigator, by regulation, retains the ability to use all information collected prior to the revocation of subject authorization. For subjects that have revoked authorization to collect or use PHI, attempts should be made to obtain permission to collect follow-up safety information (e.g. has the subject experienced any new or worsened AEs) at the end of their scheduled study period.

The data collection system for this study uses built-in security features to encrypt all data for transmission in both directions, preventing unauthorized access to confidential participant information. Access to the system will be controlled by a sequence of individually assigned user identification codes and passwords, made available only to authorized personnel who have completed prerequisite training.

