10.1 Analysis sets

10.1.1 Full Analysis Set

The Full Analysis Set (FAS) comprises all patients to whom study treatment has been assigned by randomization (EPO or EPO+DFX). According to the intent to treat principle, patients will be analyzed according to the treatment they have been assigned to during the randomization procedure.

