2.3 Analysis sets

The analysis will consider the following populations:

Full Analysis Set: The Full Analysis Set (FAS) comprises all patients to whom study treatment has been assigned by randomization (EPO or EPO+DFX). According to the intent to treat principle, patients will be analyzed according to the treatment they have been assigned to during the randomization procedure.

Safety Set: The Safety Set includes all randomized patients who received at least one dose of study medication, i.e. either EPO or EPO+DFX, and with at least one post-baseline safety assessment (e.g. lab, vital signs, AEs) and the statement that a subject did not experience an AE can currently be regarded as a valid safety assessment.

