D03	≥50% decrement from maximum response levels in granulocytes or platelets but patient not withdrawn	Report as PD, include in FAS and Safety Set.
D04	Reduction of Hb level ≥1.5g/dL compared to best response but patient not withdrawn	Report as PD, include in FAS and Safety Set.
D05	Consent withdrawn but patient not withdrawn	Report as PD, Exclude from all analyses.
S12	Deferasirox dose was not reduced despite serum creatinine increase of ≥33% above baseline and above ULN at 2 consecutive occasions	Report as PD, include in FAS and Safety Set.
S13	Deferasirox treatment was not interrupted despite severe case of skin rash	Reported as PD, include in FAS and Safety Set.
S14	Deferasirox treatment was not interrupted despite persistent and progressive increase in serum transaminase levels that cannot attributed to other causes	Report as PD, include in FAS and Safety Set.
S15	Deferasirox treatment was not interrupted despite unexplained cytopenia	Report as PD, include in FAS and Safety Set.
S16	Deferasirox dose not recalculated despite > 10% change in body weight	Report as PD, include in FAS and Safety Set.
S17	Deferasirox treatment was not interrupted despite severe hypersensitivity reactions	Reported as PD, include in FAS and Safety Set.
S18	Deferasirox treatment was not permanently discontinued despite suspected Stevens Johnson syndrome	Report as PD, include in FAS and Safety Set.
G01	Use of local laboratory instead of central laboratory	Report as PD, include in FAS and Safety Set.
G03	Patient was randomized with missing central lab results and/or based on local lab results	Reported as PD, include in FAS and Safety Set.

The RAP module 8 will include variables that will flag the missing values at baseline for the laboratory parameters or flag corresponding to certain assessments which leads to the exclusion of the patient from any analyses.

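### SAP deviation code D05 drops a randomised patient who withdrew consent but was kept on study from every analysis, contrary to the FAS and Safety Set definitions

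*SAP*

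**What the plan says.** SAP 4.4, Table 4-7, lists each protocol deviation with its effect on the analysis sets. Code D05 is "Consent withdrawn but patient not withdrawn" and its action is "Report as PD, Exclude from all analyses".

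SAP 2.3 says that the FAS "comprises all patients to whom study treatment has been assigned by randomization (EPO or EPO+DFX"). Protocol 10.1.1 has the same definition and adds: "According to the intent to treat principle, patients will be analyzed according to the treatment they have been assigned to during the randomization procedure". The Safety Set (SAP 2.3, protocol 10.1.2) takes in randomised patients who had any study drug and a safety assessment after baseline. None of these definitions mentions consent.

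Two protocol sections bear on the same patient. Section 7.1.3.1 makes withdrawal from the study mandatory once consent is withdrawn. Section 9.1, on revoked authorization to use protected health information, says that the investigator "retains the ability to use all information collected prior to the revocation of subject authorization".

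**The concern.** A programmer cannot apply Table 4-7 and SAP 2.3 together: one removes the patient and the other keeps every randomised patient. The SAP's primary analysis (2.9.1.2) is on the FAS alone, and SAP 2.3 defines no second efficacy set in which the effect of the removal could be seen.

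D05 also has no date limit. A patient may have weeks of haemoglobin values and adverse events recorded under valid consent, and all of these go. At stake are a randomised comparison altered by an event after randomisation, and safety tables that omit a treated patient.

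**Working it through.** **The rules side by side**

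| Situation | Source | Effect on sets |
|---|---|---|
| Randomised | SAP 2.3, protocol 10.1.1 | In FAS, no exception |
| Randomised, dosed, later safety assessment | SAP 2.3, protocol 10.1.2 | In Safety Set, no exception |
| Consent withdrawn, patient withdrawn from study | Protocol 7.1.3.1; not a D05 case | Stays in FAS, and in Safety Set if qualified |
| Consent withdrawn, patient kept on study | D05 | Out of all analyses |
| Other withdrawal criteria met, patient kept on study | D01 to D04, D12 | In both sets |
| Consent not given before study start | I01 | In both sets |
| No written consent at all | I24 | Out of all analyses |

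Three things follow.

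1. Rows 3 and 4 describe patients who differ only in whether the site acted on the withdrawal. Set membership therefore turns on a site error made after randomisation.
2. D05 and I24 are the only codes with full exclusion. In I24 written consent never existed; in D05 it did, up to a date. I24 therefore gives no reason to remove the data collected before that date.
3. I01 keeps a patient who had not consented when the study began, while D05 deletes one who consented and later withdrew.

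**Size (illustration only)**

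The plan states no figure on this point. Inputs: about 60 patients (SAP 2.11) randomised 1:1 (SAP 3.2), taken as n = 30 per arm, and the SAP 2.11 reference rate of 40%, so x = 12 responders.

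- As randomised, x/n: 12/30 = 40.0%
- One non-responder removed, x/(n − 1): 12/29 = 41.4%, up 1.4 points
- One responder removed, (x − 1)/(n − 1): 11/29 = 37.9%, down 2.1 points

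For the difference between arms, take the SAP's 20-point scenario: 18/30 on the combination against 12/30 on EPO. The Agresti-Caffo interval uses p̃ = (x + 1)/(n + 2) in each arm, with variance p̃(1 − p̃)/(n + 2) per arm.

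| Combination vs EPO | Difference | 95% interval |
|---|---|---|
| 18/30 vs 12/30 | 0.200 | −0.053 to 0.428 |
| 18/29 vs 12/30 (one combination non-responder removed) | 0.221 | −0.035 to 0.448 |
| 17/29 vs 12/30 (one combination responder removed) | 0.186 | −0.069 to 0.418 |

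Removing one EPO-arm patient gives the same two results with the roles exchanged: 18/30 − 12/29 = 0.186 for a non-responder and 18/30 − 11/29 = 0.221 for a responder. SAP 2.11 prints −0.04 to 0.44 for this scenario. That is what comes out if 0.60 and 0.40 are used directly as p̃ with n + 2 = 32; it does not affect the present point.

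**The case against.** The best defence is that D05 is narrow. A reader might infer that anyone who withdraws consent is deleted. The wording does not support that: the code needs both a withdrawal of consent and a failure to withdraw the patient from the study. For the same reason, it is tempting to say that D05 removes patients for poor tolerability or lack of effect in an open-label trial. Those are plausible reasons for withdrawing consent, but D05 is triggered by the site's failure to act, and nothing in the documents ties that failure to outcome. The direction of any bias is unknown.

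The defence can also say that protocol 9.1 is no rule to analyse. That stands. It concerns authorization to use health information, and it permits rather than instructs. It supports keeping the earlier data by analogy only. The consent form, which may say what happens to data on withdrawal, is a separate document (protocol 11.3) and is not available here.

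I24 also departs literally from an all-randomised FAS, and keeping it concedes that a consent-based exclusion can be acceptable. That is fair, but it supports an exception for consent never given, not the deletion of data gathered under consent.

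A reader might go on to set the last sentence of SAP 4.4, where flags are tied to a condition "which leads to the exclusion of the patient from any analyses", against code G03, "Patient was randomized with missing central lab results and/or based on local lab results", whose action is inclusion. That contradiction is not established. The sentence defers to RAP module 8, and it can be read as flagging patients who cannot enter a particular analysis that needs a baseline value. G03 governs set membership, which is a different matter.

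Lastly, it would be too strong to say that a D05 patient's adverse events vanish. SAP 2.10.1 and 2.10.2 have all safety data listed, and the SAP does not say whether D05 reaches the listings. The summary tables are affected; the listings may not be.

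**Conclusion.** The contradiction holds on the text alone. D05 cannot be applied without breaking the FAS and Safety Set definitions in both documents, and it discards data from the period of valid consent. Excluding what was collected after the withdrawal is defensible; excluding what came before is not justified anywhere in the plan.

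The effect is probably small. The documents give no expected count, and it may be zero. With 30 per arm and 12 responders assumed, one case moves that arm's rate up 1.4 or down 2.1 points, depending on the patient's response. A reader might note that removing three combination-arm non-responders in the 20-point scenario gives 18/27 against 12/30, a difference of 0.267 (0.006 to 0.492), and conclude that D05 can decide the result. The documents do not support that: nothing suggests three cases, all in one arm and all non-responders, and this is a pilot reported by estimate and interval. The reason to act is that the rule is inconsistent and cheap to correct.

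**What to change.** Change the D05 action in Table 4-7 to: *Report as PD; include in FAS and Safety Set using data up to the date of consent withdrawal; exclude data collected after that date.* Leave I24 unchanged.

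Response is then judged on haemoglobin values up to the cut-off, and the patient stays in the denominator under the general rule for percentages in SAP 2.5. If the consent form requires earlier data to be removed, write the exception and its reason into SAP 2.3, so that the set definition and the table agree.

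The cost is one line of SAP text, plus a recorded date of consent withdrawal for any D05 patient. No change to visits or sample size is needed.

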4.5 Other rules

Percentages in shift tables cross-tabulating baseline versus post-baseline values will be based on all patients with a non-missing post-baseline value in the respective analysis set.

4.6 Number of decimals

Whenever possible, minimum and maximum will be presented to the same precision as the raw data. Mean and median will be presented to one more decimal place and standard deviation to two more decimal places.

Unless stated otherwise, no imputation for missing data will be performed.

5 References

Agresti and Caffo (2000). Simple and Effective Confidence Intervals for Proportions and Differences of Proportions Result from Adding Two Successes and Two Failures. *The American Statistician*, Vol 54, No. 5.

Clopper, C. J., and Pearson, E. S. (1934), 'The Use of Confidence or Fiducial Limits Illustrated in the Case of the Binomial', *Biometrika* 26, 404–413.

6 SAS procedure used for inferential analysis

6.1 Clopper-Pearson (Exact) CI for response rate

The $100 \times (1 - \alpha \text{ level})$ % Pearson-Clopper CI for the proportion of responders (binary outcome = 1 or “Yes”), for a given treatment group **X**, is obtained from the following:

```
PROC FREQ data = dataset;
WHERE group = 'X';
TABLE binary event /binomial (exact level='Yes')
alpha = alpha level;
```

When there are no responders for treatment group **X**, SAS does not produce a CI by default. To obtain a CI in this situation, PROC FREQ is used as specified above except changing **level="No"**. From the results of this modified procedure, the values in percent of the LCL and UCL of a 0% response rate are calculated as follows:

- $LCL_{LEVEL="Yes"} (\%) = 100\% - UCL_{LEVEL="No"} (\%)$
- $UCL_{LEVEL="Yes"} (\%) = 100\% - LCL_{LEVEL="No"} (\%)$

6.2 Agresti-Caffo CI for difference in proportions

The Agresti-Caffo confidence limits for the risk difference are computed as:

$$\tilde{d} \pm (z_{\alpha/2} \times \text{s.e}(\tilde{d}))$$

where $\tilde{d} = \tilde{p}_1 - \tilde{p}_2$, $\tilde{p}_i = (n_{i1} + 1)/(n_{i.} + 2)$,

$$\text{se}(\tilde{d}) = \sqrt{\tilde{p}_1(1 - \tilde{p}_2)/(n_{1.} + 2) + \tilde{p}_2(1 - \tilde{p}_1)/(n_{2.} + 2)}$$

and $z_{\alpha/2}$ is the $100(1 - \alpha/2)$ percentile of the standard normal distribution.

That is: $\tilde{p}_1 = (n_{11} + 1)/(n_{1.} + 2)$ and $\tilde{p}_2 = (n_{22} + 1)/(n_{2.} + 2)$

	Column 1	Column 2	Total
Row 1	n_{11}	n_{12}	$n_{1.}$
Row 2	n_{21}	n_{22}	$n_{2.}$
Total	$n_{.1}$	$n_{.2}$	n

The Agresti-Caffo interval adjusts the Wald interval for the risk difference by adding a pseudo-observation of each type (success and failure) to each sample. See Agresti and Caffo (2000) for more information.

This CI calculation is available in SAS Version 9.3 using the CL=AC options as follows:

```
ods select PdiffCLs;  
ods output PdiffCLs=ciac;  
proc freq data= dataset;  
    tables group*response /riskdiff (CL=AC);  
run;
```
